8.2.2 Initiating PSV

Guidelines for the administration of sedation and analgesia are provided, (see section 8.4.1) with a strong recommendation for using the lowest possible dose of sedating drugs in both arms (or none at all) as required to keep the patient calm and cooperative, avoiding over-sedation whenever possible.

Prior to initiating PSV, record the patient's respiratory rate, heart rate, blood pressure, tidal volume (V_{te}) and minute ventilation (VE). The baseline vital signs will be needed to determine if the patient is developing signs of respiratory distress. The baseline V_t and VE required to maintain a normal pH (>7.32) will be used to monitor if the patient is developing a respiratory acidosis or respiratory alkalosis.

PSV is initiated at the following settings:

- PS level: start at 10-20 cmH₂O (or start at level patient was on prior to randomization)
- Inspiratory trigger: per clinician
- Expiratory trigger: 25% of peak inspiratory flow (default)
- PEEP: start at previous level patient was on prior to randomization
- FiO_2 : start at previous level patient was on prior to randomization

Alarm settings:

- Ppeak (Paw max): Per clinician
- RR max: 38 b/min
- Vte max: 12 mL/kg IBW
- Vte min: 0 mL
- VE max: 20 L/min
- VE min: 5 L/min
- Apnea setting: 20 s

8.2.3 Adjusting PSV

Adjustments are made to ventilator settings immediately (5 minutes) after initiating PSV and at a minimum every 8 hours thereafter (minimum, see above). If pH on arterial blood gas (ABG) is outside of the target range of 7.32-7.47, serial adjustments should be made immediately post ABG and ABG's repeated every 30-60 minutes post ventilator adjustments until pH is back within the target range or patient meets criteria to switch to A/C.

The algorithm to adjust pressure support is based on usual clinical parameters, keeping the RR \leq 35 breaths/minute and Vte 5-10 mL/kg PBW, while maintaining a pH of 7.32-7.47. Some patients may be able to be supported within this target range comfortably on pressure support, while others may not be able to tolerate pressure support without developing clinical signs of respiratory distress. Therefore, adjustments are made to the ventilator settings according to whether Respiratory Distress is present or absent.

The study protocol **defines Respiratory Distress as the presence of 2 or more** of the following signs:

Definition of Respiratory Distress

At least 2 of the following:

1. SpO₂ <90%
2. Sustained (>5 min) respiratory rate >35 b/min
3. Heart rate >140 b/min or a sustained (>5 min) increase of 20% from baseline
4. Systolic blood pressure >180 or <80 mmHg and/or systolic BP changes >30% from baseline
5. Increased anxiety
6. Use of accessory muscles
7. Complaint of dyspnea
8. Diaphoresis

Immediately after initiating PSV, and at least every 8 hours (minimum, see above) while on PSV, determine if adjustments need to be made to the ventilator settings.

Adjusting PSV if Respiratory Distress is present:

If Respiratory Distress is present, complete the following steps:

1. Treat any apparent cause of respiratory distress (eg. Secretions, bronchospasm, pulmonary edema, metabolic acidosis)
2. Increase pressure support in steps of 2-3 cmH₂O until respiratory distress resolves and pH>7.32
3. Increase PEEP and/or FiO₂ as needed to keep SpO₂ 90-96%
4. Switch to A/C mode if one or more of the following occur during steps 1-3:
 - a. Pressure support >20 cmH₂O
 - b. Pressure support + PEEP > 30 cmH₂O

- c. $\text{FiO}_2 > 60\%$ required to maintain $\text{SpO}_2 \geq 90\%$
- d. Clinical Instability**
- e. Requiring neuromuscular blockade and/or sedation such that patient is no longer able to trigger the ventilator

Definition of Clinical Instability

Any 1 of the following:

1. Unstable hemodynamic status (SBP < 80 mmHg) with or without vasoactive drug
2. Vasopressor requirements > 0.5 $\mu\text{g}/\text{kg}/\text{min}$ epinephrine/norepinephrine or equivalent
3. Active cardiac ischemia (dynamic ST changes on cardiac monitor or electrocardiogram)
4. Unstable arrhythmias (HR > 140 or < 50) with clinical signs of low cardiac output or SBP < 80 mmHg)
5. Uncontrolled hypertension (SBP > 180 mmHg)
6. Abrupt decrease in the level of consciousness (RASS -4 or -5 or SAS 1 or 2)
7. Dangerous agitation (RASS +4 or +3 or SAS 7)
8. Metabolic (or mixed) acidosis with pH < 7.32
9. Emergency situation that merits return to full ventilation (A/C) according to best clinical judgement

Patients requiring A/C ventilation should be reassessed within 24 hours for **Criteria for Switching from A/C to PSV**.

Adjusting PSV if Respiratory Distress is Absent:

If respiratory distress is absent, adjust the level of pressure support, PEEP and FiO_2 as follows:

1. Adjust the PEEP according to clinical judgment at the bedside
2. Adjust the FiO_2 to the lowest level required to maintain $\text{SpO}_2 > 90\%$ and in the range 90-96%.
3. If patient appears comfortable (RR 12-35 and Vt 5-10 mL/kg PBW): target range achieved.
No adjustments required unless one of the following occurs:
 - a. If RR < 12 or > 35 or Vte < 5 or > 10 mL/kg PBW, obtain arterial blood gas (ABG):
 - i. If ABG demonstrates respiratory alkalemia, treat any apparent cause of hyperventilation (eg. pain, anxiety, metabolic acidosis), then decrease PS in steps of 2-3 cmH₂O until pH < 7.47 OR Vte < 8 mL/kg PBW
 - ii. If ABG demonstrates respiratory acidemia OR respiratory distress develops:
 1. Increase PS in steps of 2-3 cmH₂O until pH > 7.32 and respiratory distress resolves
 2. Switch to A/C mode if one or more of the following occur during above steps:
 - a. PS > 20 cmH₂O
 - b. PS + PEEP > 30 cmH₂O
 - c. $\text{FiO}_2 > 60\%$ required to maintain $\text{SpO}_2 \geq 90\%$
 - d. Clinical Instability**
 - e. Requiring neuromuscular blockade and/or sedation such that the patient is no longer able to trigger the ventilator

Patients requiring A/C ventilation should be reassessed within 24 hours for **Criteria for Switching from A/C to PSV**.

8.2.4 Resuming PSV after A/C ventilation

Patients switched to A/C ventilation as per study protocol should be reassessed within 24 hours, and at least once daily thereafter, for **Criteria for Switching from A/C to PSV**. If all of the criteria for switching from A/C to PSV are present, the patient **must** be tried on PSV: follow the Initiation of PSV protocol, with initial and subsequent adjustments made to PSV setting according to Algorithm for Adjusting PSV. After a trial of PSV, patients may be switched back to A/C mode if they meet criteria according to the PSV ventilation strategy algorithm. The **Criteria for Switching from A/C to PSV** are as follows:

Criteria for Switching from A/C to PSV:

1. Able to trigger ventilator breaths
2. On assist/control with the following settings:
 - a. AC/VC: P_{plat} ≤ 30 cmH₂O with V_t 6-8 ml/kg OR
 - b. AC/PC: PC+PEEP ≤ 30 cmH₂O
3. PaO₂ ≥ 60 mmHg or SpO₂ ≥ 90% on FiO₂ ≤ 0.60 and PEEP ≤ 15 cm H₂O
4. Metabolic disorders corrected; pH > 7.32
5. Stable hemodynamic status: stable or decreasing doses of vasopressors for ≥ 6 hours
6. Absence of **Clinical Instability** (see definition, above)

8.3 Procedures Common to Both Groups

8.3.1 Weaning from Mechanical Ventilation

Weaning will be conducted in the same way in the two arms. The PSV level or the PAV+ %Support will **not** be used to assess readiness to wean. **At a minimum, patients in both arms will be assessed at least once daily for Criteria to Initiate Weaning, and will undergo the weaning trials at least once daily if criteria at each stage of weaning are met.** However, additional screening, additional pre-SBT readiness assessments, or additional SBTs may be performed at any time at the physician's discretion or as per institutional standard.

Criteria to Initiate Weaning:

1. SpO₂ ≥ 90%
2. FiO₂ ≤ 0.40
3. PEEP ≤ 8
4. pH ≥ 7.32
5. vasopressor requirements no higher than norepinephrine 0.1 µg/kg/min or equivalent and at a stable or decreasing dose ≥ 6 hours
6. No Respiratory Distress (see definition)
7. No Clinical Instability (see definition))

If all criteria are present except PEEP > 8 cmH₂O, decrease PEEP to ≤ 8 cmH₂O and if all criteria still present after 30 min, proceed to next step, the pre-SBT readiness assessment.

Pre-SBT screening test (ZERO CPAP Trial)

Patients meeting above Criteria to Initiate Weaning will undergo a Pre-SBT readiness assessment to measure the Rapid Shallow Breathing Index (RSBI) as follows:

1. With patient's ETT connected to the ventilator circuit, change the ventilator mode to CPAP at 0 cmH₂O and FiO₂ 0.40
2. Monitor patient for 2 min
3. On the ventilator, assess the f/V_t ratio after 1-2 minutes at 0 cmH₂O CPAP:

4. FAIL: If the $f/V_t > 100$, or $SpO_2 < 90\%$ or Clinical Instability, patient has failed the ZERO CPAP trial and will not proceed to SBT. Resume ventilation according to assigned ventilation algorithm at the ventilator settings used immediately prior to the CPAP test.
5. PASS: If the f/V_t is ≤ 100 , and $SpO_2 \geq 90\%$, proceed to SBT

SBT

Patients who pass the Pre-SBT readiness assessment, will proceed to SBT as follows:

1. Disconnect endotracheal tube from ventilator circuit and place patients on T-piece* with FiO_2 0.40. (For patients with tracheostomy, place patients on tracheostomy mask trial with FiO_2 0.40)
2. Monitor patient for 30-120 minutes:
3. FAIL/ SBT Termination: Terminate the SBT and return patient to ventilator settings according to assigned algorithm if at any time one of the following occur:
 - a. Respiratory Distress
 - b. Clinical Instability
 - c. Increased somnolence with elevated pCO_2 and/or $pH < 7.32$
4. Pass: Patients will be considered to have passed the SBT if, after a minimum of 30 minutes and maximum of 120 minutes, none of the failure/SBT termination criteria have occurred. Proceed to evaluate patient for extubation criteria (or disconnection criteria for patients with tracheostomy, see below)

**for the purposes of this study, the Sponsor considers SBT performed with patients connected to ventilator on flow-by with CPAP of 0 cmH_2O and FiO_2 0.40 to be equivalent to SBT performed on T-piece with FiO_2 0.40.*

Extubation Criteria:

Patients are assessed for extubation criteria after successfully passing an SBT:

1. Criteria to initiate weaning still present
2. Passed SBT
3. A level of consciousness sufficient to ensure airway protection (as judged by the clinician)
4. A cough strong enough to clear secretions (as judged by the clinician) and not requiring suctioning more than every 2 hours

Note that Extubation Criteria do not need to be present prior to performing the pre-SBT assessment or the SBT. Patients who pass the SBT AND meet Extubation Criteria should be extubated immediately (within 2 hours). Extubation may be deferred (up to a maximum 24 hours after meeting all extubation criteria) if a procedure or surgery that will require intubation is planned within 24 hours or at the discretion of the treating physician (justification must be provided on the eCRF). In the event that extubation is deferred (beyond 2 hours from time of meeting extubation criteria), patients must be reassessed for extubation criteria within 24 hours and either extubated or justification provided on the eCRF on a daily basis for any further deferrals. Patients who pass the SBT but do NOT meet Extubation Criteria are returned to ventilator settings according to the assigned algorithm and reassessed for Extubation Criteria at least once daily. SBT will be repeated as needed, or as indicated by the clinician. If, upon reassessment, the Criteria to Initiate Weaning are no longer present, patients will continue on the assigned ventilation strategy and undergo daily assessments to restart the weaning process from the beginning.

In sites where Maximal Inspiratory Pressure (MIP) and Maximal Expiratory Pressure (MEP) are routinely measured prior to extubation and recorded in the medical chart, these scores will be collected as part of the eCRF.

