Patients on A/C ventilation (or similar mode) or PAV or on pressure support >20 cmH₂O will be assessed daily and will undergo a daily Pressure Support Trial, provided none of the Pressure Support Deferral Criteria are present.

In the presence of any of the Pressure Support Trial Deferral Criteria, the pressure support trial may be deferred up to 24 hours. Patients should be reassessed at least daily and can proceed to the Pressure Support trial after discussion with the site PI, provided the patient still passes Criteria C and no deferral criteria are present. If deferral criteria remain present, the Pressure Support Trial may be deferred on a daily basis after daily reassessment.

Once no deferral criteria are present, patients proceed as follows:

- Patients already on pressure support of ≤20 cm H₂O for >30 minutes will be considered to have passed the Pressure Support Trial and will move on to the next stage of enrolment
- Patients on A/C mode or similar mode or PAV or on pressure support >20 cmH₂O will undergo the Pressure Support Trial

The Pressure Support Trial (PST) is conducted as follows: patients will be placed on PSV 5-20 cmH₂O (above PEEP) for at least 30 minutes under direct clinical observation, at the same PEEP and FiO₂ settings they were on prior to the PST. The maximum settings allowed for the PST are a pressure support of 20 cmH₂O or PS+PEEP=30 cmH₂O. The PST can be stopped at any time for prolonged apnea, Respiratory Distress or Clinical Instability (see definitions below). At the end of 30-120 minutes, an arterial blood gas will be drawn.

Patients fail the Pressure Support Trial if they develop prolonged apnea, Respiratory Distress, Clinical Instability (see definitions below), or require PS >20 cmH₂O, PS + PEEP > 30 cmH₂O, or require FiO₂>60% to maintain SpO₂>90%, or respiratory acidosis with pH <7.32 despite maximum PS of 20 cmH₂O. The PST is terminated immediately upon reaching any failure criteria. Patients who fail a PST are returned to their previous ventilator settings or settings that restore respiratory comfort. Patients who pass the PST may remain on pressure support 5-20 cmH₂O.

Definition of Respiratory Distress

At least 2 of the following:

1. SpO₂ <90%
2. Sustained (>5 min) respiratory rate >35 b/min
3. Heart rate >140 b/min or a sustained (>5 min) increase of 20% from baseline
4. Systolic blood pressure >180 or <80 mmHg and/or systolic BP changes >30% from baseline
5. Increased anxiety
6. Use of accessory muscles

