1. Disconnect endotracheal tube from ventilator circuit and place patients on T-piece* with FiO₂ 0.40. (For patients with tracheostomy, place patients on tracheostomy mask trial with FiO₂ 0.40)
2. Monitor patient for 30-120 minutes:
3. FAIL/ SBT Termination: Terminate the SBT and return patient to prior ventilator settings if at any time one of the following occur:
 - a. Respiratory Distress
 - b. Clinical Instability
 - c. Increased somnolence with elevated pCO₂ and/or pH<7.32
 - d. Desaturation with SpO₂ <90% on FiO₂ 0.40

**for the purposes of this study, the Sponsor considers SBT performed with patients connected to ventilator on flow-by with CPAP of 0 cmH₂O and FiO₂ 0.40 to be equivalent to SBT performed on T-piece with FiO₂ 0.40.*

Following the SBT, proceed to the final stage (E).

In the final stage (E), patients will be considered eligible for randomization if the following criteria are met.

E. Randomization Inclusion Criteria

C1.	Patient/SDM has provided consent OR Plan to obtain deferred consent as Patient incapable and no SDM available to provide consent within the randomization window
E1.	Upon review of Criteria A, B, and C, the patient still passes and the patient has passed the PST.
E2.	Does not meet Weaning Criteria OR Fails the ZERO CPAP Trial OR Fails the SBT

E. Randomization Exclusion Criteria:

B9	Patient has met enrolment inclusion criteria B1-B5 AND has tolerated pressure support of 0-20 cm H ₂ O or proportional assist ventilation of 0-85% ≥24 consecutive hours (including time on CPAP, t-piece, or tracheostomy mask). Note (1): It is acceptable to include a patient who has been tried on pressure support or proportional assist ventilation but has required pressures >20 cmH ₂ O or assistance >85% or has required return to A/C ventilation within the 24 hour time window; Note (2): B9 does not apply to patients while on ECMO
C4.	Patient/SDM has declined consent
C5.	Patient incapable and no SDM available to provide consent (not applicable if plan to obtain deferred consent)

E3.	Passed SBT on t-piece, FiO ₂ 0.40 for 30-120 minutes
E4.	Approval withdrawn (by physician or patient/SDM)

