8.3.6 Tracheostomy

Tracheostomy may be performed in either group when clinically indicated. Notwithstanding, there is no proven benefit to early tracheostomy and therefore we encourage clinicians to delay decisions regarding elective tracheostomy until day 10 post randomization.

Disconnection Procedure for Patients with Tracheostomy

For patients with tracheostomies, SBT will be performed on tracheostomy mask, with FiO₂ 0.40. Tracheostomized patients who pass their initial SBT by completing 120 minutes of tracheostomy mask trial shall remain off the ventilator and on tracheostomy mask trial provided they do not develop any criteria for SBT termination. Tracheostomized patients who fail their initial SBT within 120 minutes may undergo gradual increments in tracheostomy mask trials according to local ICU site practice, provided local standards of care are applied equally to patients regardless of treatment group. When not undergoing tracheostomy mask trials, patients should be ventilated according to their assigned ventilation strategy, until successful termination of invasive MV is achieved. “Successful extubation/termination of invasive mechanical ventilation” will be defined as remaining off of invasive ventilation for 7 consecutive days, or discharge from hospital. Decanulation will be decided based on local practices.

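### The post-randomization SBT failure list (Protocol 8.3.1) omits stand-alone desaturation, which fails the eligibility SBT (7.3); the gap matters mainly for tracheostomized patients

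*Protocol*

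**What the plan says.** The protocol describes the SBT twice.

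- **Before randomization (7.3).** The trial is stopped as a failure on any one of four items, a to d. Items a to c are Respiratory Distress, Clinical Instability, and increasing somnolence with a raised pCO2 and/or a pH under 7.32. Item d is "Desaturation with SpO₂ <90% on FiO₂ 0.40".
- **After randomization (8.3.1).** The instruction is "Terminate the SBT and return patient to ventilator settings according to assigned algorithm if at any time one of the following occur". Items a to c are repeated and there is no item d. The next step defines a pass: after 30 to 120 minutes, "none of the failure/SBT termination criteria have occurred".

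In 8.3.1 the SBT follows a ZERO CPAP trial of two minutes. An SpO2 under 90% is enough on its own to end that trial: "patient has failed the ZERO CPAP trial and will not proceed to SBT".

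After a pass, 8.3.1 sends intubated patients to the extubation criteria and tracheostomized patients to disconnection criteria further on. Section 8.3.6 supplies the latter. Patients who complete 120 minutes on the mask "shall remain off the ventilator and on tracheostomy mask trial provided they do not develop any criteria for SBT termination". For the others: "Tracheostomized patients who fail their initial SBT within 120 minutes may undergo gradual increments in tracheostomy mask trials according to local ICU site practice", with the assigned ventilation strategy in between.

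**The concern.** Items a to c match and only item d is absent, with no reason given in the protocol or SAP. The neighbouring steps (the Criteria to Initiate Weaning and the ZERO CPAP trial) each carry an SpO2 limit that acts alone. This looks more like a drafting slip than a choice.

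What is at stake is mainly patient safety in a small group. For a tracheostomized patient the list decides the pathway: stay off the ventilator, or return to it with graded mask trials. A patient whose only problem is low saturation is sent to the first.

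A lesser matter is consistency. A failed SBT is defined by four items for the pre-randomization subgroup (SAP 6.5) and by three for the post-randomization weaning outcomes.

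**Working it through.** The plan states no figure on this point, so the check is a comparison of rules. Take a patient whose only abnormal finding is SpO2 under 90% on FiO2 0.40.

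| Rule | Place | Content | Result for this patient |
|---|---|---|---|
| Eligibility SBT | 7.3 | 4 items (a–d); d is desaturation | Fails |
| ZERO CPAP trial | 7.3 and 8.3.1 | SpO2 <90% is sufficient alone | Fails |
| Post-randomization SBT | 8.3.1 | 3 items (a–c) | Depends on a–c |
| – item a, Respiratory Distress | defined in 7.3 | 8 signs, 2 needed; SpO2 <90% is 1 | Not met (1 < 2) |
| – item b, Clinical Instability | defined in 7.3 | 9 items, 0 name SpO2 | Not met, unless item 9 (emergency, clinical judgement) is invoked |
| – item c, somnolence with high pCO2 and/or low pH | 8.3.1 | No SpO2 element | Not met |
| Extubation criterion 1 | 8.3.1 | Weaning criteria still present, including SpO2 ≥90% | Not extubated |
| Disconnection procedure | 8.3.6 | 0 SpO2 criteria of its own | Stays off the ventilator |

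**Step 1: is the item really absent?** 4 − 3 = 1 item, and it is stand-alone desaturation. The numbering in 8.3.1 moves from item c directly to step 4, so nothing suggests a lost line.

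**Step 2: does another item catch it?** Respiratory Distress requires "At least 2 of the following", and low saturation supplies one. Clinical Instability has no SpO2 threshold. So no listed threshold is met, and the pass rule in 8.3.1 is satisfied.

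**Step 3: what happens next?** An intubated patient meets the SpO2 check at the extubation criteria and, if still below 90%, returns to the assigned ventilator settings. A tracheostomized patient has no equivalent check. Section 8.3.6 refers to criteria for SBT termination without naming a section. It stands beside 8.3.1 under the procedures common to both groups, so the three-item list is the natural reading. The four-item list in 7.3 carries the same label and also mentions the tracheostomy mask, so the other reading is possible.

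**Step 4: compare the two post-randomization tests.** The SBT is 30/2 = 15 to 120/2 = 60 times as long as the ZERO CPAP trial, yet has the weaker oxygenation rule. This ratio shows the inconsistency. It does not measure risk or the number of patients.

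**The case against.** The strongest case against is that the practical effect is close to nil.

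- Intubated patients are covered by extubation criterion 1.
- The remaining tracheostomized patients must have low saturation and none of the other seven distress signs, shortly after holding SpO2 at 90% or more on zero CPAP.
- SpO2 is monitored continuously in both groups (8.3.3). Clinical Instability item 9 lets a clinician return the patient to full ventilation, and 11.1 puts patient safety first in an emergency.
- The two SBTs also serve different ends. In 7.3 a failure qualifies the patient for randomization; in 8.3.1 a pass opens the way to liberation. The lists need not be identical.
- The change may have no one left to apply to. Planned enrolment ran to September 2021, and the SAP cites sources accessed in July 2024.

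Most of this stands and limits the size of the point. It does not remove it. Monitoring and judgement set no threshold, whereas 8.3.6 says that the patient shall remain off the ventilator. Different purposes could justify different lists, but neither document says so, and the step that leads to liberation is the less obvious place to relax an oxygenation limit. The possible end of enrolment does not make the written rule right.

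**Conclusion.** The inconsistency is real and worth correcting, but narrow. As written, isolated desaturation is a failure at the eligibility SBT and in the ZERO CPAP trial, and a pass at the post-randomization SBT. The practical exposure is to tracheostomized patients. Its frequency is not given and cannot be derived; it is probably small. The conclusion assumes that 8.3.6 means the 8.3.1 list.

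Three stronger readings are tempting, and the documents support none of them.

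- **Bias between arms.** A reader might infer that the shorter list favours one arm. The weaning rule is the same in both, and nothing in the documents shows that isolated desaturation would differ between them.
- **False liberations.** A reader might infer that lenient passes inflate the primary endpoint. Liberation requires sustained freedom from invasive ventilation: 7 days in SAP 5.1, or in Protocol 9.2 the earliest of 7 days, successful ICU discharge or live hospital discharge. An SBT pass alone creates no event. Time to first successful SBT would be touched more directly, but SAP 6.2 treats it mainly descriptively.
- **No other safeguard.** A reader might infer that tracheostomized patients are kept off the ventilator on the three-item list and nothing else. Section 8.3.6 does not name its list, and continuous monitoring and clinical judgement still apply.

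**What to change.** Add item d to the SBT failure list in 8.3.1, worded as in 7.3 ("Desaturation with SpO₂ <90% on FiO₂ 0.40"), and have 8.3.6 refer explicitly to the 8.3.1 list. Apply the change prospectively, without re-coding SBTs already done.

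Leave the handling of brief dips during later tracheostomy mask time to the investigators. The five-minute qualifier on the respiratory-rate and heart-rate signs should not be carried over: no document applies it to SpO2, and 8.3.6 does not restate FiO2 0.40 for mask time after the SBT.

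The cost is one list item and one cross-reference. No new monitoring is needed, since 8.3.3 already requires continuous SpO2. The downside is that a few more SBTs will be stopped, under the same rule in both arms.
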